5.3 Exploratory Outcome Measures

There are a number of exploratory outcomes which include:

- (i) Neutrophil activation biomarkers which may include but are not limited to measurement of plasma MPO and MMP-8.
- (ii) Plasma and serum inflammatory response biomarkers which may include but are not limited to measurement of CRP, cytokines (including but not limited to TNF α , IL-1 β , IL-6, IL-8), proteases and anti-proteases, adhesion and activation molecule expression (including but not limited to sICAM-1), NETs, coagulation factors (including but not limited to thrombin-anti-thrombin complex, tissue factor, protein C, thrombomodulin and plasminogen activator inhibitor-1), RAGE ligands and vitamin D status specific cellular populations within the blood (using but not limited to cytopins and flow cytometry) and identification of transcriptome changes within these cell populations.
- (iii) Pulmonary and systemic epithelial and endothelial function and injury will be assessed by the following: Plasma and serum biomarkers which may include but not be limited to measurement of RAGE, Ang I/II, SP-D, vWF and PCP3 will be undertaken. Urinary albumin/creatinine ratio will also be measured.
- (iv) Samples from subjects will also be tested on primary cultures of fresh human neutrophils monocytes and macrophages as well as mesenchymal stromal cells to determine surrogate markers of inflammation which may include but not be limited to the measurement of activation (shape change, CD11b surface expression, superoxide release), adhesion and transmigration, cytokine release and MMP production, rate of apoptosis and their ability to phagocytose.

6. STUDY DESIGN

6.1 Study Design

This is a prospective, observational, multi-centre blinded diagnostic accuracy study of a novel multiplex PCR test. Site research and clinical teams will be blinded to results obtained by multiplex PCR; these results will be compared to those from conventional microbiological methods observed in the course of standard care in ICU.

6.2 Study Setting

At least 15 adult intensive care units (ICU) across the UK will participate.

6.3 Study Schematic Diagram

[figure not shown]

Figure 1: Study Schematic for the TEST-IT trial

6.4 Study Timeline

Table 1: Study Timeline Gantt Chart

Year	1												2						3								
Quarter	Q1			Q2			Q3			Q4			Q5		Q6		Q7		Q8		Q9						
Period end month	1	2	3	4	5	6	7	8	9	10	11	12	13	14	15	16	17	18	19	20	21	22	23	24	25	26	27
Trial Stage	Pre-clinical	Set up	Lead-in	Main study																		Analysis/report					
Technology Development	X																										
Recruit Staff	X	X																									
Ethics Approval		X																									
Sponsor Approval		X																									
Local R&D Approvals		X	X	X	X	X																					
Site Training & Initiation		X	X	X	X	X	X	X																			
Patient Recruitment		X	r/v	X	X	X	r/v	X	X	X	X	X	X	X	X	X	X	X	X	X	X	X	X	X	X	X	X
Number of Sites Open		1	3	3	6	6	9	9	12	12	>15	>15	>15	>15	>15	>15	>15	>15	>15	>15	>15	>15	>15	>15	>15	>15	
Sample Accrual		4	22	54	113	204	317	471	647	864	1103	1383	1673	1988	2303	2618	2933	3248	3563	3878	4193	4501					
Assessments:																											
Blood sampling		X	X	X	X	X	X	X	X	X	X	X	X	X	X	X	X	X	X	X	X	X	X	X	X	X	X
Data Entry		X	X	X	X	X	X	X	X	X	X	X	X	X	X	X	X	X	X	X	X	X	X	X	X	X	X
TMG Meetings	X	X	X	X	X	X	X	X	X	X	X	X	X	X	X	X	X	X	X	X	X	X	X	X	X	X	X
TSC Meetings		X			X					X						X						X					
Site Close Down																					X	X	X	X			
Data Analysis																					X	X	X				
Health Economics Analysis																					X	X	X				
Study Report																								X	X		
Dissemination																									X	X	X

6.5 End of Study

For the purposes of submitting the end of trial notification to the Sponsor and REC the end of trial will be considered to be when database lock occurs for the final analysis.

The trial will be stopped prematurely if:

- Mandated by the Research Ethics Committee (REC)
- Mandated by the Sponsor (e.g. following recommendations from the Trial Steering Committee (TSC))
- Funding for the trial ceases

The REC that originally gave a favourable opinion of the trial will be notified in writing once the trial has been concluded or if terminated early.

7. PATIENT ELIGIBILITY, SCREENING AND RECRUITMENT

7.1 Eligibility Criteria

Patients will be screened for eligibility based on the inclusion/exclusion criteria outlined below.

7.1.1 Inclusion criteria:

1. Patients with suspected sepsis undergoing blood sampling for culture in the course of routine care.

7.1.2 Exclusion criteria:

1. Patients aged <16 years old.
2. Patients previously recruited to the study.
3. Consent declined.

7.2 Co-enrolment Guidelines

Patients enrolled in any other studies are potential candidates for this study. This is at the Principal Investigator's (PI) discretion and should be considered when the burden on participants is not expected to be onerous. Co-enrolment with any studies should be documented in the Case Report Form (CRF).

7.3 Screening Procedure

Adult patients admitted to ICU who undergo blood culture testing for suspected sepsis are eligible for this study and will be screened daily, on the basis of the inclusion/exclusion criteria as specified in the protocol.

The Clinical Trials Unit (CTU) will provide screening logs which must be completed by the PI or designee to document all patients screened for the study and all patients recruited. Patients screened and not recruited on to the study should also be documented on the screening log, including the reason for not being enrolled on the study. The PI or designee will be required to submit screening logs to the CTU approximately every month.

7.4 Recruitment

In order to estimate the overall sensitivity of the test 4501 samples are required and will be tested to assess the diagnostic accuracy of the Multiplex PCR test. This will be achievable given the high incidence of suspected sepsis in the critically ill and the large number of patients expected to meet the eligibility criteria. Each patient can contribute more than one sample to this study; however an interval of at least 5-days must lapse between consecutive samples obtained.

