11. STATISTICAL CONSIDERATIONS

11.1 Sample Size

The sample size is based on:

- (i) an assumed 10% event rate for true positive results among specimens collected – this is based on pilot data collected in a single centre.
- (ii) an estimated overall test sensitivity of 90%, and specificity of 95%.
- (iii) the need to ensure that the overall test sensitivity is estimated with a high degree of precision. We have set this precision as +/-3%, at the 95% confidence level.
- (iv) the ability to assess performance of the test for detecting pathogens for which true positive results are expected as infrequently as 1 in 500 tests. We have set the precision for this as +/-20%, at the 95% confidence level
- (v) Given a 10% event rate for true positive results, a sample size that achieves the proposed degrees of precision for the sensitivity estimate will enable the specificity of the test to be measured with even greater precision.

With an assumed sensitivity of 90% with a 10% true positivity rate, in order to estimate the overall sensitivity of the test with a precision of +/-3% at the 95% confidence level, 3851 samples are required. For uncommon pathogens, with an assumed sensitivity of 90% with a 0.2% true positivity rate, in order to estimate the overall sensitivity of the test with a precision of +/-20% at the 95% confidence level, 4501 samples are required. Therefore, 4501 samples will be tested to assess the diagnostic accuracy of the test using these parameters.

The sample has not been inflated for dropouts or missing data because: (i) research sampling is not necessary after the day of enrolment; (ii) the follow-up period is very short; and (iii) the nature of ICU care presents minimal risk of attrition for follow-up.

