11.2 Statistical Methods

Data will be analysed by the Study Statistician. Results will be presented as 2x2 tables for the whole study population. The sensitivity and specificity of POC testing are the main constituents of the primary outcome measure of the study. An assessment of the diagnostic accuracy of the POC device will be based on these measures and on positive and negative predictive values calculated from comparison with conventional culture as the reference standard. The data supporting an assessment of diagnostic accuracy will be reported according to STARD³⁸ criteria, including explanations of losses of participants. The possible effects of heterogeneity in the study population will be examined and separate sub-analyses for the different types of patients recruited will be performed. These will provide assessments of the validity of POC testing by this method and device in the context of prior antimicrobial exposure, varying underlying diagnoses and by patient condition.

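### Repeat samples per patient are allowed, but exclusion 2 and part of section 11.1 read as one sample per patient, and the stated precision assumes independent samples

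*Protocol*

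**What the plan says.** Section 7.4 of the protocol sets the target in samples and allows repeats: "Each patient can contribute more than one sample to this study; however an interval of at least 5-days must lapse between consecutive samples obtained". It gives no cap and no expected number per patient. Section 9.2.1 also foresees later samples, because the additional 10 ml is drawn only with a patient's first sample.

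Other passages read as if each patient gives one sample:

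- Exclusion criterion 2 (section 7.1.2) is "Patients previously recruited to the study", with no exception for further samples from someone already enrolled.
- Section 11.1 declines to inflate the sample size, first because "research sampling is not necessary after the day of enrolment".
- Section 11.3 removes the participant, not the sample, when a PCR or culture result is absent.

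Section 11.1 counts specimens. It takes "an assumed 10% event rate for true positive results among specimens collected" and a sensitivity of 90%, and concludes that "in order to estimate the overall sensitivity of the test with a precision of +/-3% at the 95% confidence level, 3851 samples are required". A second calculation, for rarer organisms, uses a positivity of 0.2%, the same sensitivity and a precision of ±20%. It arrives at 4501, which becomes the target. Section 11.2 adds: "Results will be presented as 2x2 tables for the whole study population". It names no interval method. Section 5.1 promises 95% confidence limits.

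**The concern.** There are two linked problems.

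The first is the sampling unit. A site that screens daily against exclusion 2 as worded could screen out an enrolled patient at the next blood culture, while another site takes a further sample under 7.4. The mix of samples would then depend on how each site reads the criterion. A statistical analysis plan cannot repair that.

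The second is precision. Two samples from one patient, taken five or more days apart, may share the same persistent or relapsing infection. If their results correlate, 4501 samples carry less information than 4501 independent ones, and the precision promised in 11.1 is optimistic. What matters is how much correlation each target can absorb before it is missed.

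**Working it through.** **Inputs from section 11.1.** Sensitivity 0.90; positivity 10% overall and 0.2% for an uncommon pathogen; half-widths 0.03 and 0.20; 95% confidence, z = 1.96.

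**Reproducing the plan's figures.** For one proportion with independent samples, positives needed = z² × Se × (1 − Se) / d², and total samples = positives / positivity.

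- Overall: 3.8415 × 0.09 / 0.0009 = 384.15, rounded up to 385; 385 / 0.10 = 3850 (stated 3851).
- Uncommon pathogen: 3.8415 × 0.09 / 0.04 = 8.64, rounded up to 9; 9 / 0.002 = 4500 (stated 4501).

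Both agree to within one sample, with a design effect (DE) of 1. There is no allowance for repeat samples.

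**Precision at 4501 samples, independent.**

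- Overall: 450.1 positives; 1.96 × √(0.09 / 450.1) = 2.77%.
- Uncommon pathogen: 9 positives; 1.96 × √(0.09 / 9) = 19.6%.

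**Largest design effect each target tolerates** (positives available / positives needed).

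- Overall, ±3%: 450.1 / 384.15 = 1.17.
- Uncommon pathogen, ±20%: 9 / 8.64 = 1.04.

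**Range under assumed clustering.** DE = 1 + (m − 1) × ICC, where m is the mean number of culture-positive samples per patient who has any, and ICC is the within-patient correlation. The half-width is multiplied by √DE. The protocol gives neither m nor ICC, so the values below are assumptions.

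| m | ICC | DE | Overall sensitivity | Uncommon pathogen |
|---|---|---|---|---|
| 1.0 | any | 1.00 | ±2.77% | ±19.6% |
| 1.1 | 0.3 | 1.03 | ±2.81% | ±19.9% |
| 1.2 | 0.5 | 1.10 | ±2.91% | ±20.6% |
| 1.5 | 0.3 | 1.15 | ±2.97% | ±21.0% |
| 1.5 | 0.5 | 1.25 | ±3.10% | ±21.9% |
| 2.0 | 0.5 | 1.50 | ±3.39% | ±24.0% |

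**How much repetition this takes.** If repeats come as pairs, DE = 1 + f × ICC, where f is the share of positives that belong to a pair.

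- Overall, ±3% is lost when f × ICC exceeds 0.17: f of about 57% at ICC 0.3 (0.17 / 0.3), or about 34% at ICC 0.5.
- For an uncommon pathogen, one pair among nine positives is f = 2/9 = 0.22. At ICC 0.3, DE = 1 + 0.22 × 0.3 = 1.07 and the half-width is 19.6 × √1.07 = 20.2%, already over the target.

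**The case against.** The passages can be read together. Exclusion 2 governs recruiting a patient, and 7.4 governs samples from a patient already in the study. Section 10.2 allocates a single identifier at recruitment, and 9.2.1 expects later samples. Likewise, saying that later sampling is not necessary does not say that it never happens. This reading is natural and probably intended, so the conflict is one of wording and can be resolved. But the protocol does not state it, and the criterion is what sites apply.

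On precision, only repeated culture-positive samples affect sensitivity. With 10% positivity and a five-day gap, m may be close to 1. For overall sensitivity this largely stands: the 4501 target exceeds the 3851 needed, and the milder scenarios all meet ±3%. It helps less for uncommon pathogens, where a single pair can matter.

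A reader might infer three stronger claims that the documents do not support:

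- **That the plan analyses samples as independent.** A 2x2 table is a form of presentation. No interval method is named, and the analysis plan, not shown here, may specify patient-clustered limits.
- **That the specificity claim in 11.1(v) fails.** It says only that specificity will be more precise than sensitivity. Under independence specificity is ±0.67% (1.96 × √(0.0475 / 4050.9)). At DE 1.5 it is ±0.82%, against ±3.39% for sensitivity.
- **That clustering by ICU badly undermines the intervals.** The protocol gives no site-level correlation and no site sizes, so any such figure rests on outside assumptions.

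**Conclusion.** The point holds in limited form. Section 7.4, exclusion 2 and the first no-inflation reason in 11.1 do not fit together as written and must be reconciled. The sample sizes are independence calculations for a design that does not guarantee independent samples.

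The two targets are unequally exposed. The ±3% for overall sensitivity survives a design effect up to 1.17. The ±20% for a 1-in-500 pathogen, which sets the sample size, is missed above 1.04. It would be wrong to conclude that either target will be missed: the direction is clear if within-patient correlation is positive, but its size cannot be derived from the protocol. The figures use the plan's own normal-approximation formula, which is rough with nine positives, and an assumed range for m and ICC.

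**What to change.** 1. **Sections 7.1.2 and 11.1.** Clarify that exclusion 2 bars re-enrolment of a patient under a new identifier, and does not bar repeat samples under 7.4 from an enrolled patient under the same identifier. Keep the bar on re-enrolment: without it a patient could acquire two identifiers, and the link needed for clustering would be lost. Remove or reword the first no-inflation reason in 11.1.
2. **Section 11.1.** State that the ±3% and ±20% figures assume independent samples, and show them over a range of design effects, for example 1.0 to 1.5.
3. **Section 11.2.** State that the sample is the unit of analysis and that the primary 95% limits allow for clustering by patient, by cluster bootstrap or robust variance. Add a sensitivity analysis on the first sample per patient. If the analysis plan already does this, a cross-reference is enough. Clustering by site can be an optional sensitivity analysis.

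The cost is a minor amendment and possibly slightly wider intervals. No extra patients are needed.

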8. INFORMED CONSENT

The consultation and recruitment of patients lacking capacity is regulated by different legal jurisdictions across the sites of this study. Practice will adhere to local regulations as outlined below.

It is the responsibility of the Principal Investigator (PI) (or designee) to ensure that informed consent is obtained for each participant. Consent may be obtained by the PI; an appropriately trained Research Nurse; or medically trained investigator. The PI (or designee) taking informed consent must be GCP trained, suitably qualified and experienced and have been delegated this duty by the Principal Investigator on the delegation log.

A Covering Statement, Patient Information Sheet and Consent Form approved by the Research Ethics Committee (REC) will be provided to each study site. Wherever possible, consent will be taken directly from the patient, however, the incapacitated nature of patients in intensive care units will usually preclude obtaining prospective informed consent from participants.

For patients who are unable to give informed consent due to the effects of sedation, infection, delirium and mechanical ventilation; consent or personal/nominated consultee

opinion will be obtained as outlined below and in line with the legal requirements for patients without capacity in England and Wales (Mental Capacity Act 2005), and in Scotland (Adults With Incapacity (Scotland) Act 2000). Consent processes in Northern Ireland follow common law. For the purposes of the trial, the consent processes used in England and Wales will be used in Northern Ireland.

At all sites other than those in Scotland, a deferred consent process will be applied. Samples will be taken as outlined in section 9 of this protocol and will be held at site pending consent being obtained for inclusion in the study. Patients or their personal/ nominated consultee will have 48 hours to decide whether or not to take part in the study. No sample will be tested or further stored without consent having first been obtained. If after providing consent a participant subsequently loses capacity, personal / nominated consultee opinion will be obtained as outlined below.

In Scotland consent from the patient or nearest relative / welfare attorney may be obtained after admission to ICU but prior to meeting study inclusion criteria.

8.1 Personal Consultee - England, Wales and Northern Ireland

The researcher will seek advice from a Personal Consultee (who may be a relative, partner or friend of the participant). This should normally take place during a face-to-face meeting. An authorised staff member/researcher will describe the trial to the individual, and provide them with a Covering Statement, Information Sheet and Declaration Form for Personal Consultee (England/Wales and Northern Ireland). The researcher will seek their views about whether the patient should take part in the study. They will be asked about their opinion of the wishes and feelings of the patient if they had capacity.

After the researcher has checked that the information sheet is understood, the researcher will invite the Personal Consultee to sign the form and will then countersign it. A copy of the form should be placed in the patient's medical notes and a copy filed in the Investigator Site File (ISF).

If the Personal Consultee is not available at site, the researcher may contact the Personal Consultee by telephone and seek verbal agreement. This verbal agreement will be recorded in the Consultee Telephone Agreement Form. The Consultee Telephone Agreement Form will be signed by a second member of staff who has witnessed the telephone consent. This witness may be a member of the site study team or site medical staff. A copy of the Consultee Telephone Agreement Form should be placed in the patient's medical notes and a copy filed in the ISF. Written agreement will then be obtained as soon as possible.

8.2 Nominated Consultee - Approval by a Registered Medical Practitioner (RMP) - England, Wales and Northern Ireland

In the event that there is no Personal Consultee for sites in England, Wales and Northern Ireland, authorisation to recruit the patient will be sought from a RMP (a doctor unrelated to the study conduct). The RMP will be informed about the trial by a member of the research team and given a copy of the Registered Medical Practitioner Form (England/Wales and Northern Ireland) and a copy of the Information Sheet. If the RMP decides that the patient is suitable for entry into the study they will be asked to complete the relevant authorisation form. A copy of the authorisation form should be placed in the patient's medical notes and a copy filed in the ISF. In the event that a Personal Consultee is identified after the RMP has provided their opinion, the above process for Personal Consultee will be followed and all forms will be filed as instructed above.

For sites in Scotland where no Welfare Guardian / relative is available it will not be legally possible to enroll the patient (specific to the Adults with Incapacity Act Scotland for non-CTIMP trials).

8.3 Nearest Relative / Welfare Attorney – Scotland

In Scotland consent from the patient or nearest relative / welfare attorney may be obtained after admission to ICU but prior to meeting study inclusion criteria.

The researcher will seek consent from a Nearest Relative / Welfare Attorney (who may be a relative, partner or friend of the participant). This will usually take place during a face-to-face meeting. An authorised staff member/researcher will describe the trial to the individual, and provide them with a Covering Statement, Patient Information Sheet and Consent Form for Nearest Relative/Guardian or Welfare Attorney (Scotland). The researcher will seek their views about whether the patient should take part in the study. They will be asked about their opinion of the wishes and feelings of the patient if they had capacity

After the researcher has checked that the information sheet is understood, the researcher will invite the Nearest Relative / Welfare Attorney to sign the form and will then countersign it. A copy of the form should be placed in the patient's medical notes and a copy filed in the ISF.

8.4 Patient Consent to Continue - England, Wales and Northern Ireland

Site research staff as delegated by the PI will assess whether the patient has regained capacity to give informed consent. Patients may be approached either whilst still in ICU or within 48-96hrs after discharge from ICU to obtain permission to continue in the study.

The consent to continue process will include providing the Covering Statement, Patient Information Sheet and Consent Form and allowing sufficient time for the patient to understand the material and ask questions. If the patient agrees to continue in the study they will be asked to sign the Consent Form which will then be counter signed by a member of the research team.

If the participant declines on-going participation in the study no further follow-up will take place. Data collected up until that point will be anonymised before returning to the co-ordinating centre. In the rare event that the patient does not regain capacity or the staff have been unable to obtain consent to continue, the opinion provided by the Personal/Nominated Consultee or consent from the Nearest Relative/ Guardian or Welfare Attorney will continue.

